6.3 Randomisation

The feasibility RCT will involve randomisation. Following consent and the completion of the brief ET screening tool and baseline assessments, participants will be individually randomised 1:1 to intervention versus social care as usual, stratified by prison (prison 1, prison 2) and age group ($<50, \ge 50$). Randomisation should occur as soon as possible after baseline, but within one week.

The randomisation sequence, using variable blocks sizes, will be generated by a statistician independent to the trial team and implemented through a secure web-based system on REDCap, which will ensure concealment of allocation to blinded members of the research team. Only site staff who have been delegated the role of randomisation on the delegation log will be able to access the randomisation system. An automated confirmation email will be generated when a participant is randomised and sent to the CIs and other delegated members of the study team.

Prisoners allocated to the intervention arm will then complete the ET assessment. This strengths-based assessment of social care need will be conducted by an ET worker. Strengths and assets-based approaches to assessment and care planning focus on capabilities, explore help available from wider support networks, and take into account issues important to the individual (56). Those with higher-level social care needs based on the ET assessment will receive the ET intervention, whilst those with lower-level social care needs will be given tailored advice and information about appropriate resources or services. We will clarify the definitions of higher and lower level social

care needs as part of our preliminary training development workshops. This definition will also be dependent on the individual processes established at the prison.

6.4 Blinding

In the feasibility RCT, blinding of care providers and participants will not be possible because of the differences between the intervention and social care as usual. Research staff conducting the quantitative data collection and entry at 42- and 90-days (±7 days), as well as those performing the health economic and statistical analysis, will be blinded. At the start of each data collection session, participants will be asked not to discuss the intervention they received with the research team. If unblinding does occur, this will be recorded on the participant's Case Report Form (CRF).

Safety reporting will be managed by the PIs and is unlikely to lead to unblinding of data collection, entry, and analysis staff. Emergency unblinding will not be required in this study.

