2. OBJECTIVES AND OUTCOME MEASURES

The aims of WP1 (development work) and WP2 (feasibility RCT and embedded formative process evaluation) are to address the following research questions:

- 1. Can we implement the ET intervention in two men's prisons?
- 2. Is it acceptable and feasible to conduct an RCT to assess whether ET improves the number of met social care needs for adults in prison who are likely to have unmet needs after six weeks and three months, in comparison with care as usual?

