The acceptability of the measures in the following table will be assessed. These measures were determined using a literature review (PDG, NIHR 202610):

Outcome	Measurement Tool	Measurement Method	Baseline	42-Days (±7 days)	90-Days (±7 days)
Unmet needs in forensic settings	CANFOR-R	Researcher completes in person with prisoner	~	~	~

The Camberwell Assessments of Needs-Forensic Research (CANFOR-R) is a semi-structured interview schedule assessing need in 25 domains. Each domain has 4 sections, covering the absence or presence of needs, formal and informal help needed and received, overall satisfaction with help, and links between need and offending. The CANFOR-R has been used in previous RCTs in prisons settings (35). It is the only measure that: has adequate evidence for content validity, development, and relevance for our population, and has been designed as a progress measure (51). However, the tools ability to measure change in need has not been fully assessed (51). We will explore its responsivity, including an analysis of domains relevant to this population, such as needs relating to communication, day-time activities, education, physical health, selfcare, and social contact. We will apply the Met Needs Index to CANFOR-R scores for relevant domains (52).

Adult social care outcomes	ASCOT SCT4	Researcher completes in person with prisoner	~	~	>
		prisoner			

The Adult Social Care Outcomes Toolkit (ASCOT) SCT4 is a 32-item self-complete measure of adult social care related quality of life across eight dimensions: accommodation cleanliness and comfort, control over daily life, dignity, food and drink, occupation, personal cleanliness and comfort, personal safety, and social participation and involvement. Each question has

Health Research Authority

four response options relating to four outcome states (ideal, no needs, some needs, high-level needs). Raw scores are then converted into numbers that reflect the relative value of that outcome to the general population. Scores range from -0.17 to 1.00, with higher scores indicating better quality of life. We will use this measure to assess adult social care outcomes. We will also assess its suitability to calculate incremental cost per quality adjusted life year (QALY) for a full economic evaluation. This will include analysing data to estimate parameters (means and standard deviations) and explore responsivity. We will also evaluate the extent to which this measure aligns with changes in the CANFOR-R.

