The Recovering Quality of Life (ReQoL-10) is a 10-item self-report measure assessing quality of life during recovery for people with different mental health conditions. Items have been drawn to cover areas of quality of life that are important for service users, such as activity (meaningful), belonging and relationships, choice, control and autonomy, hope, self-perception, well-being, and physical health. Each item has five response options, which are allocated scores between 0 and 4. The ReQoL-10 is scored by summing scores across questions. Total scores range from 0 to 40, where a higher score indicates a better quality of life. We will use this measure to assess recovery. We will also assess its suitability to calculate incremental cost per QALY for a full economic evaluation. This will include analysing data to estimate parameters and explore responsivity. Finally, we will evaluate the extent to which this measure aligns with changes in the CANFOR-R.

Resource Use Questionnaires Person with prisoner
--

Resource use questionnaires that have previously been developed and tested in community samples (53) will be used to assess receipt of health, personal, and other care services. These will be completed based on care plans, case notes, and discussions with prisoners.

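### The blinding instruction in section 6.4 asks participants not to discuss the intervention they received, although the same follow-up sessions ask what help and services they have had

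*Protocol*

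**What the plan says.** Section 6.4 blinds "Research staff conducting the quantitative data collection and entry at 42- and 90-days (±7 days"), together with the health economic and statistical analysts. Participants and care providers cannot be blinded. The safeguard for the assessor is a request made as each session opens: "participants will be asked not to discuss the intervention they received with the research team". If the blind is broken, this is noted on the case report form (CRF).

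Section 2.2 describes CANFOR-R as an interview on 25 domains, each "covering the absence or presence of needs, formal and informal help needed and received, overall satisfaction with help", plus links with offending. Its mode is "Researcher completes in person with prisoner". The resource-use questionnaires "will be used to assess receipt of health, personal, and other care services" and draw on care plans, case notes and conversation with the prisoner. The section 6.5 schedule places both at day 42 and day 90.

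Section 7 describes what the intervention arm receives. People with higher-level needs get an ET worker who draws up a care plan with them, liaises with services, refers and advocates. People with lower-level needs get tailored advice and signposting.

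**The concern.** The instruction does not separate two things: which group the participant is in, and what help they have had. The blind requires only the first to be withheld. The instruments require the second to be reported. In the intervention arm the two overlap, because ET-worker contact, care planning and advocacy are forms of help.

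A participant who follows the request literally may omit that help from the CANFOR-R help and satisfaction sections and from the service-use answers. A participant who answers fully may show the assessor which arm they are in. The protocol gives neither the participant nor the assessor a rule for this. Recording unblinding on the CRF captures disclosure but does nothing about answers held back.

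This matters because the trial is meant to produce information about these measures: whether CANFOR-R responds to change, how the other measures align with it, how variable each candidate outcome is, how well resource use can be collected, and how great the risk of bias is. The full trial's question would be "whether ET improves the number of met social care needs for adults in prison", so the wording could be carried into a setting where arms are compared.

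**Working it through.** No figure in the protocol depends on this point, so the check sets the provisions side by side.

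1. **Timing.** The request is made at the start of each session (6.4). At baseline it has no content, since randomisation follows baseline (6.3). It therefore matters at days 42 and 90, when the assessor is blinded.

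2. **What is asked next.** In those sessions the researcher completes CANFOR-R face to face, including help received and satisfaction with it (2.2, 6.5). Resource use is scheduled at the same visits and rests partly on what the prisoner says (2.2, 6.5).

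3. **Whether a truthful answer can describe the intervention.** Section 7 lists care-plan coproduction, coordination, referral and advocacy by the ET worker. An intervention-arm participant asked about formal help could properly name any of these. Help arranged through others, such as a cell adaptation or peer support, can be named without mentioning ET.

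4. **Whether anything resolves the overlap.** Sections 6.4, 6.5 and 2.2 contain no rule on reporting or coding ET-worker help under the instruction. The only related provision is the CRF note of unblinding, and no point in the session is given for it.

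5. **Who must interpret the request.** Sections 5 and 6.2 deliberately include people who lack capacity, and section 6.2 notes lower literacy and more cognitive impairment than in the community. The intended limit of the request should not be left for them to infer.

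6. **Exposure.** Planned intervention arm 38 (9.1) × 2 follow-ups = 76 sessions at most. This ceiling assumes no attrition and counts signposted participants, who have less ET help to report. The split between ET and signposting is unknown, because section 6.3 leaves the definition of higher and lower need to be clarified.

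7. **What can be affected.** The help, satisfaction and service-use answers are affected directly. Section 2.2 applies the Met Needs Index to CANFOR-R but does not show how the index uses the help sections, so an effect on the index is an inference. Section 9.2 rules out statistical comparison of the arms, so no treatment-effect estimate from this trial is at risk.

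The documents give no rate of withholding or unblinding, so none is calculated.

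**The case against.** The strongest reply is that ET is largely coordination. Much of what it achieves reaches the prisoner through health, prison, local authority, third-sector or peer services, and both arms continue with usual social care (12.9). A participant can report handrails or a peer supporter without naming ET. This stands. A reader might infer that every intervention-arm answer must be either incomplete or unblinding, but the documents support that dilemma only for direct ET-worker contact.

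A reader might also infer that controls are untouched and that the result is a bias against ET. Neither is established. Some controls could take the phrase to cover their usual care, and disclosure could push ratings in the other direction from omission.

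Three further points limit the harm. Resource use also draws on care plans and case notes, so omissions at interview can be partly corrected. ET's own delivery cost comes from the fidelity tool (9.2), not from recall. The primary outcomes are feasibility outcomes and CANFOR-R is listed as secondary; it is the reference against which the other measures are judged, but it is not designated as the lead outcome.

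Finally, script wording and order of administration are often left to assessor guidance, and evaluating risk of bias is already an objective (2.1). That would answer a complaint about missing detail. Here the protocol states the instruction itself, and as stated it conflicts with what the instruments ask.

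**Conclusion.** The concern holds as a conflict between a stated instruction and the content of the instruments used straight after it. Followed literally, the request discourages valid answers about help, satisfaction and services, mainly in the intervention arm; answered in full, those items can reveal allocation. At most 76 intervention-arm follow-up sessions are exposed. The frequency, size and direction of the effect cannot be derived from the documents.

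The conclusion assumes that at least some participants would count ET-worker contact as help received, which section 7 makes reasonable, and that some would take the request at face value. It does not depend on any assumed rate. The consequence is limited to the quality of the help, satisfaction and service-use data, the responsivity and variability estimates, and the procedure passed on to a full trial. Because the correction costs little and a feasibility trial is the place to test it, it should be made before follow-up begins.

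**What to change.** **Section 6.4.** Replace the request with: *Please tell us about all the help and services you have had, but please do not tell us which study group you are in.*

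**Section 6.5.** Fix the order at days 42 and 90: ASCOT SCT4, EQ-5D-5L, ICECAP-A and ReQoL-10 first; then CANFOR-R; resource use last. The four self-report measures are then completed before the questions most likely to reveal allocation. Keep CANFOR-R intact. Rating need for all domains first and returning for the help sections would mean two passes through 25 domains with a population that has more cognitive impairment, and the protocol does not show that need can be rated apart from help.

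**CRF.** Have the assessor record whether they have been unblinded immediately before CANFOR-R and again at the end of the session. This shows how much unblinding the instruments themselves cause.

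**Cost.** One reworded sentence, one line on order and one extra CRF item. The fixed order removes some flexibility in the interview. Some disclosure through direct ET-worker contact will remain, but it will be measured.

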6.6 Participant Retention

Attrition will be minimised by asking for transfer holds for all participants for the duration of their time in the feasibility RCT (with their consent) and requesting community contact details and/or permission to contact them through the National Probation Service. If prisoners are transferred, we will attempt to follow them up in other prisons in the estate. If prisoners are released into the community, we will offer them options for completing the study measures through digital means, face-to-face or telephone interviews, or on paper. We will also measure numbers of participants who exit the study through release or transfer, as this will inform the feasibility of a full RCT.

6.7 Qualitative Interviews

Qualitative interviews will be conducted for the process evaluation to inform the development of case studies and an understanding of the barriers and enablers to acceptability and feasibility of the RCT. Interviewees will include prisoners from both the control and intervention arms (N=20), ET workers (N=2) and supervisors (N=2), and healthcare, prison, and local authority staff (N=20).

Development of Case Studies

Individual case studies will be developed for approximately N=10 prisoners in the feasibility RCT (N=4 in the ET intervention group, N=2 in the ET signposting group, and N=4 in the control group). Case studies will be based on both realist-informed interviews and observations. Purposive sampling will be used to identify prisoners who are diverse in terms of their age, disability status, ethnicity, mental and/or physical health conditions, offence types, sentence length, and social care needs. Prisoners within the ET intervention group will be invited to interview once in their first month of receiving ET and once in their last month. Those within the ET signposting group will be invited to interview once in their first month of receiving signposting and again around two months later. Prisoners in the control arm will be interviewed once during the study period. For each individual case study, one member of prison staff (N=10 total) and one member of healthcare staff (N=10 total) will be interviewed. In addition, approximately two members of local authority staff will be spoken to at each site (N=4 total). These interviews will take place around the same time as the second interview for prisoners in the intervention arm and the sole interview for prisoners in the control arm. Finally, ET workers (N=2) and their supervisors (N=2) will be interviewed twice, once within the first three months of the ET delivery period, and once within the last three months. Staff will be identified through a mix of purposive and snowball sampling.

The case studies will allow us to capture in-depth information about those in the intervention and control groups, from their own and staff perspectives.

For case studies relating to the intervention arm, interviews will first focus on the 'theory gleaning' phase of realist evaluation, where the IPT is tested in a real-world setting (57). Questions will ask about if the ET intervention or signposting has been delivered as intended (feasibility and fidelity), how it has been received (acceptability) and what outcomes prisoners and staff have experienced. These questions will not be explicitly realist in their phrasing, but will aim to elicit answers about the context, mechanisms, and outcomes of the intervention. Additional questions will focus on the 'theory refinement' phase, where a teacher-learner cycle is adopted between the interviewer and participant (57). The previously outlined context, mechanisms, and outcomes, and initial IPT (58) will be presented to participants, who will then accept, reject, or update these theories. This will allow us to better understand what aspects of the intervention work, in what circumstances, for whom, and how. Second interviews for prisoners and ET staff will comprise similar questions, but will ask about any changes since the first interview. This will allow us to understand whether identification and delivery of social care under ET changes over time.

For case studies relating to the control arm, interviews will focus on how social care is delivered in prisons. Similar to the ET arm, the interviews will focus on whether social care is delivered as intended, how it is accepted by people in prison, who it works for, how, and why.

Case studies will also be informed by focused and time-limited ethnographic observations of the case study participants. Additional consent for these observations will be sought from prisoners and staff members involved in the case studies. Focused observations will be conducted of each person undertaking discrete, time-limited activities or tasks (for example, educational activities, exercise, focused work, mealtimes, and interactions with ET and prison staff, as appropriate) and detailed field notes will be made. Field notes will record the place, time, and setting of the activity or task, and what happened during the observation. The researchers will ensure that only details from observations concerning consented individuals will be recorded; field notes will not detail actions, interactions, or speech with prisoners or staff who do not provide consent. Observations will add context to the experiences of people who may not be able to fully express themselves through interviews, and highlight experiences that may be avoided or overlooked.

Understanding Barriers and Enablers

A further five prisoners at each site will participate in interviews that explore barriers and enablers to acceptability and feasibility of the intervention and trial design (e.g., randomisation, outcome measures, and potential contamination between the control and two intervention groups). This will enable the evaluation of the research design, and refinement of the delivery platform.

Participation will be entirely voluntary, and the researchers conducting the process evaluation will differ from those collecting baseline data and other study assessments.

6.8 Withdrawal Criteria

For WP1 and WP2, the PIS will explain that participants are able to decline or withdraw from the study if they wish to, without giving a reason and without prejudice to future care. The reasons for deciding to withdraw are varied; participants may, for example, find that they are no longer willing to engage in the research, or have other programmes that they would prefer to prioritise. Their

reasons for discontinuation will be requested and recorded in REDCap in a withdrawal form, but their right not to state a reason will be respected. Data collected from the participant prior to their withdrawal will remain on REDCap. The characteristics of the participants who withdraw or are lost to follow-up will be compared with those that remain within the trial.

For the feasibility RCT, participants might also withdraw from the study due to being transferred or released. However, attempts will be made to minimise attrition (Section 6.6). In addition, early discontinuation will be allowed, and participants that withdraw their consent for the treatment element of the feasibility RCT can still be invited to complete the outcome measures. In addition, participants who withdraw their consent for the feasibility RCT element of WP2 can still be invited to take part in the process evaluation element of WP2.

For WP2, for participants lacking capacity to consent, if there is any indication that they do not want to take part, the researchers will prioritise their interests and withdraw them from the study. No participants lacking capacity to consent will be recruited for WP1.

6.9 End of Trial

The end of the feasibility RCT is defined as the completion of the final participant's final outcome measures. The end of the study is defined as the conclusion of the final participant's last interview or visit. At this point, the research team will submit a checkpoint report based on the progression criteria. If the minimum success criteria for key feasibility aims and objectives are achieved, the programme will progress to a full RCT. The sponsor delegate will notify the REC of the end of the trial within 90 days of completion. The final report will be written within 12 months of the end of the trial. If the trial terminates early for any reason, the CI will notify the REC of early termination (including reasons for this) or end of trial in accordance with the required timelines.

